8.3.8 Management of RO7121661 Specific Adverse Events

Based on the MoA, PD-1/TIM-3 is expected to show a safety profile that is similar to other CPIs. Toxicities from CPIs can be divided into infusion reactions and immune-mediated adverse events (imAEs). Toxicities associated or possibly associated with RO7121661 treatment should be managed according to standard medical practice. Additional tests, such as autoimmune serology or biopsies, should be used to determine a possible immunogenic etiology.

Measures will be taken to ensure the safety of participants participating in this study, including the use of stringent inclusion and exclusion criteria and close monitoring of participants during the study. Administration of RO7121661 will be performed in a monitored setting in which there is immediate access to trained personnel and adequate equipment and medicine to manage potentially serious reactions.

For events in which management guidelines are not covered in this protocol, participants should be managed as deemed appropriate by the Investigator according to best medical judgment and local medical guidelines. Clinical judgment may be applied and risk/benefit consideration may suggest deviating from these guidelines. In this specific case, decisions on study treatments will be taken by the Investigator upon consultation with the Medical Monitor.

8.3.8.1 Infusion-Related Reactions

Administration of therapeutic antibodies may cause IRRs characterized by symptoms such as fever, chills, dizziness, hypertension, hypotension, dyspnea, restlessness, sweating, flushing, skin rash, tachycardia, tachypnea, headache, tumor pain, nausea, and/or vomiting. Respiratory and cardiac symptoms such as, bronchospasm, larynx, and throat irritation, wheezing, laryngeal edema and atrial fibrillation may also occur. Such reactions typically occur during or shortly after an infusion or within 24 hours after study treatment infusion, predominantly at the first infusion. The incidence and severity typically decrease with subsequent infusions.

Participants may also develop immunoglobulin (Ig)E mediated hypersensitivity reactions. IRRs may be indistinguishable from an anaphylactic reaction; however, in case of IgE mediated hypersensitivity, symptoms typically occur after previous exposure and very rarely with the first infusion. In case of confirmed IgE mediated hypersensitivity reaction, treatment should be permanently discontinued.

No premedication is indicated for the administration of Cycle 1 of RO7121661. However, patients who experience a grade 2 or higher infusion-related reaction (IRR) with RO7121661 should receive premedication for subsequent infusions (see Section 6.1.2). In case of Grade 4 IRR related to RO7121661, the participant should be permanently discontinued from the study treatment. If an IRR occurs during the infusion of RO7121661, please refer to Table 6.

Table 6 Recommendations for RO7121661 Infusion-Related Reaction Prevention and Management

^a Infusion-Related Reactions	Guidance
Grade 1-2	Slow infusion to ≤ 50% or interrupt infusion
	Give supportive treatment ^b
	Upon symptom resolution may resume infusion (if interrupted) at 50% starting rate. The infusion must remain at the lower rate resulting in symptom resolution for the remainder of the infusion.
	For grade 2 IRRs, subsequent cycles of RO7121661 should be administered with pre-medication including acetaminophen/paracetamol and an antihistamine, such as diphenhydramine.
	Notes:
	For Grade 2 wheezing or urticaria, patient must also be pre-medicated prior to subsequent doses (as described above).
	2. If symptoms recur with the same or greater severity
	following the slower or interrupted infusion, the infusion
	must be stopped immediately. No further RO7121661
	will be administered for the cycle.
Grade 3	Discontinue infusion. No further RO7121661 will be administered for the cycle.
	Give supportive treatment ^b
	Subsequent cycles of RO7121661 should be administered with pre-medication including paracetamol, antihistamine and corticosteroids. c
	Notes:
	If symptoms recur despite pre-medications with the
	same or greater severity at subsequent cycles, the
	infusion must be stopped immediately and patient
	permanently discontinued from study treatment.
	2. Patients who experience Grade 3 wheezing,
	bronchospasm or generalized urticaria at first occurrence
	must be discontinued from study treatment.
Grade 4	Discontinue infusion immediately
	Give supportive treatment
	Permanently discontinue study treatment

- ^a Refer to the NCI-CTCAE, v5.0 scale for the grading of symptoms.
- b Supportive treatment: Patients should be treated with acetaminophen/paracetamol and an antihistamine, such as diphenhydramine, if they have not been administered in the last 4 hours. Intravenous fluids (e.g., normal saline) may be administered as clinically indicated. For bronchospasm, urticaria, or dyspnea, antihistamines, oxygen, corticosteroids (e.g., 100 mg IV prednisolone or equivalent), and/or bronchodilators may be administered per institutional practice.
- ^c Subsequent infusions may be started at the original rate in consultation with the Medical Monitor.

8.3.8.2 Immune-mediated adverse events

Most immune-mediated adverse events (imAEs) observed with immunomodulatory agents have been mild and self-limiting, however such events should be recognized early and treated promptly to avoid potential major complications. Any organ or tissue can be involved, although some imAEs occur much more commonly than others. The most frequently occurring imAEs affect skin, colon, endocrine organs, liver, and lungs. Others are very infrequent, but may be very serious, even lethal, such as neurological disorders and myocarditis.

Discontinuation of RO7121661 may not have an immediate therapeutic effect, and in severe cases, immune-mediated toxicities may require acute management with topical corticosteroids, systemic corticosteroids, mycophenolate, or TNF-α inhibitors. RO7121661 therapy may be suspended for most Grade 2 toxicities, with consideration of resuming when symptoms revert to Grade 1 or less. Corticosteroids may be administered. Grade 3 toxicities generally warrant suspension of RO7121661 and the initiation of high-dose corticosteroids (prednisone, 1-2 mg/kg/day, or methylprednisolone, 1-2 mg/kg/day). Corticosteroids should be tapered over the course of at least 4-6 weeks. Some refractory cases may require infliximab or other immunosuppressive therapy. In general, permanent discontinuation of RO7121661 is recommended with grade 4 toxicities, with the exception of endocrinopathies that have been controlled by hormone replacement. The management guidelines for imAEs associated with RO7121661 are provided in Appendix 6.

8.4 TREATMENT OF OVERDOSE

Study treatment overdose is the accidental or intentional use of the drug in an amount higher than the dose being studied. An overdose or incorrect administration of study treatment is not an adverse event unless it results in untoward medical effects (see Appendix 2 for further details).

Decisions regarding dose-interruptions or modifications will be made by the Investigator/treating Physician in consultation with the Medical Monitor based on the clinical evaluation of the participant.

In the event of an overdose, the Investigator should:

Contact the Sponsor's Medical Monitor immediately.

- Closely monitor the participant for AE/SAE and laboratory abnormalities until resolved.
- Obtain a blood sample for PK analysis within 14 days from the date of the last dose
 of study treatment, if advised by the Medical Monitor (determined on a case-bycase basis).
- Document the quantity of the excess dose, as well as the duration of the overdose, in the CRF.

For this study, any dose of RO7121661 greater than 150% of the recommended dose level will be considered an overdose.

The Sponsor does not recommend specific treatment for an overdose.

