4.1 OVERALL DESIGN

An overview of the study design is provided in Section 1.2.

Study NP40435 is a first-in-human, open-label, multicenter, Phase I multiple-ascending dose (MAD) study of single agent RO7121661. The study consists of 2 parts (A and B):

- Part A (RO7121661 Dose Escalation): To determine the MTD and/or RDE based on safety, tolerability, PK, and/or the PD profile of escalating doses of RO7121661 every 2 weeks (Q2W). If for specific cleared cohort(s) the safety, PK and/or RO and/or the biomarker profile need to be further characterized, additional participants, potentially enriched in certain indications and/or characteristics, may be enrolled.
- Part B (RO7121661 Tumor-Specific Expansion Cohorts): To evaluate anti-tumor activity of the RDE of RO7121661 from Part A (2.1 g Q2W) and to confirm safety and tolerability in participants with selected tumor types. B1, B2, B4 and B5 expansions may be staggered, sequential or concurrent. Part B3 will not proceed prior to generation of data from the initial CPI experienced indication(s):
 - Part B1: CPI experienced second line and beyond metastatic melanoma
 - Part B2: CPI and platinum experienced second or third line PD-L1 positive NSCLC
 - Part B3: PD-L1 positive, CPI naïve, first line NSCLC
 - Part B4: CPI-naïve SCLC with prior failure of, progression on, or intolerance to standard therapy
 - Part B5: CPI-naïve ESCC

Part A of the study will enroll participants with solid tumors who have progressed on a cancer therapy or who are not amenable to standard of care. At least DLT evaluable participants will be enrolled in each cohort during the dose escalation (see Section 4.1.3). Dose escalation will be carried out according to a modified continual reassessment method (mCRM) with escalation with overdose control (EWOC) design, with the aim of identifying the MTD/RDE of RO7121661.

Since RO7121661 will be administered Q2W in Part A, the cycle length will be defined as 14 days. The maximum total number of participants in the dose escalation portions of Part A1 will be approximately DLT evaluable participants on a Q2W schedule. A dose cohort can be extended to enroll additional participants (approximately), potentially enriched in certain tumor types and/or characteristics to confirm safety, PK and/or RO and/or the biomarker profile.

Part B1 and/or B2 and/or B4 and/or B5 may commence upon completion of Part A. The starting dose of RO7121661 for Part B is 2.1 g Q2W as derived from the RDE in Part A

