Human PK simulation via allometric scaling of the linear clearance data from cynomolgus monkey is consistent with an IgG-like PK, with a projected human half-life of ~19 days at target-mediated drug disposition (TMDD)-saturated doses. At lower doses, RO7121661 is predicted to show a more rapid clearance due to TMDD.

The safe starting dose is predicted to show a maximal response in an ex vivo SEB cytokine release assay up to 70% (with unknown TIM-3 contribution) which should result in pharmacological activity in participants. To support comparison of these functional assays, pembrolizumab, another PD-1 inhibitor currently on the market where tolerable doses (no DLT observed) up to 10 mg/kg Q2W were investigated, was included for benchmarking. The starting dose selected for pembrolizumab was 1 mg/kg and showed full saturation in target engagement in these assays (Patnaik et al 2015).

Compared to a classical MABEL approach, the approach used here reduces the number of participants exposed to sub-therapeutic doses of RO7121661 while ensuring that the starting-dose is in a safe range.

The initially proposed Q2W dosing interval is supported by the predicted clearance and elimination half-life ($t_{1/2}$) of RO7121661 with a projected human elimination $t_{1/2}$ of approximately 19 days.

A maximum feasible dose of 2.1 g of RO7121661 has been defined based on predicted IC $_{95}$ for PD-1/TIM-3 of approximately 320 μ g/mL and confidence in ex vivo and in vitro SEB data and benchmarking results to pembrolizumab. Based on product specifications, the dosing is currently limited to 2.1 g and must not be exceeded under any circumstances. In case dose escalation is planned to progress beyond 2.1 g, the corresponding chemistry, manufacturing, control (CMC) documents and protocol will be amended as appropriate.

Flat dosing was selected for this protocol because no strong influence of body surface area (BSA) or body weight on overall exposure is expected. On the basis of the PK data emerging from this clinical study, any potential covariates on exposure to RO7121661, such as BSA, body weight, age, ethnicity and gender will be explored in order to confirm this dosing approach.

In conclusion, a 70 mg flat dose is proposed as the starting dose of RO7121661 for Part A, on the basis of both data from nonclinical studies with RO7121661 and previous clinical experiences with PD-1/PD-L1 and TIM-3 inhibitors.

Part B

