5.2. REPORTING REQUIREMENTS FOR CASES OF ACCIDENTAL OVERDOSE OR MEDICATION ERROR

Accidental overdose and medication error (hereafter collectively referred to as "special situations"), are defined as follows:

- Accidental overdose: accidental administration of a drug in a quantity that is higher than the assigned dose
- Medication error: accidental deviation in the administration of a drug
 In some cases, a medication error may be intercepted prior to administration of the drug.

Special situations are not in themselves adverse events, but may result in adverse events. Each adverse event associated with a special situation should be recorded separately on the Adverse Event eCRF. If the associated adverse event fulfills seriousness criteria, the event should be reported to the Sponsor immediately (i.e., no more than 24 hours after learning of the event; see Appendix 2, Section 5.1). For RO7121661, adverse events associated with special situations should be recorded as described below for each situation:

- Accidental overdose: Enter the adverse event term. Check the "Accidental overdose" and "Medication error" boxes.
- Medication error that does not qualify as an overdose: Enter the adverse event term. Check the "Medication error" box.
- Medication error that qualifies as an overdose: Enter the adverse event term.
 Check the "Accidental overdose" and "Medication error" boxes.

In addition, all special situations associated with RO7121661, regardless of whether they result in an adverse event, should be recorded on the Adverse Event eCRF as described below:

- Accidental overdose: Enter the drug name and "accidental overdose" as the event term. Check the "Accidental overdose" and "Medication error" boxes.
- Medication error that does not qualify as an overdose: Enter the name of the drug administered and a description of the error (e.g., wrong dose administered, wrong dosing schedule, incorrect route of administration, wrong drug, expired drug administered) as the event term. Check the "Medication error" box.
- Medication error that qualifies as an overdose: Enter the drug name and "accidental overdose" as the event term. Check the "Accidental overdose" and "Medication error" boxes. Enter a description of the error in the additional case details.
- Intercepted medication error: Enter the drug name and "intercepted medication error" as the event term. Check the "Medication error" box. Enter a description of the error in the additional case details.

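### Section 8.4 sets two overdose thresholds, above 100% and above 150% of the dose, and the second conflicts with Appendix 2; accidental Part B infusions above 2.1 g and up to 3.15 g fall in the gap

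*Combined protocol and SAP*

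**What the plan says.** Section 8.4 (Treatment of Overdose) states twice what an overdose is. It opens: "Study treatment overdose is the accidental or intentional use of the drug in an amount higher than the dose being studied". It then lists what the investigator does after one: contact the Medical Monitor at once, monitor closely until matters resolve, take a PK sample if the Medical Monitor advises it, and document the excess. After that list comes a sentence framed as specific to this study: "any dose of RO7121661 greater than 150% of the recommended dose level will be considered an overdose".

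Appendix 2, Section 5.2 defines accidental overdose as "accidental administration of a drug in a quantity that is higher than the assigned dose", with no 150% allowance. It keeps a separate category for medication errors that fall short of an overdose, with different event terms and check-boxes on the Adverse Event eCRF.

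Two further passages set the scale. Section 4.1 says: "The starting dose of RO7121661 for Part B is 2.1 g Q2W as derived from the RDE in Part A". Section 4.4, citing product specifications, says that "the dosing is currently limited to 2.1 g and must not be exceeded under any circumstances". Its next sentence, which begins "In case dose escalation is planned to progress beyond 2.1 g", requires amended manufacturing documents and an amended protocol first.

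**The concern.** After a dosing error, a site has to decide whether the event is an overdose. Section 8.4 gives two answers, Appendix 2 agrees with only one of them, and no text ranks them. A site could reasonably take the study-specific closing sentence as the rule.

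The answer has consequences. The list of 24-hour reportable events in Appendix 2, Section 5 covers serious adverse events, non-serious events of special interest, pregnancies and DLTs, but not overdose. Appendix 2, Section 5.2 adds 24-hour reporting only when an associated adverse event is serious. For an infusion that is too large but causes no symptoms, the only overdose-specific immediate notification is therefore the one in Section 8.4, and it depends on which sentence the site applies. The same choice decides whether the eCRF shows an accidental overdose or only a medication error.

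**Working it through.** The plan prints no overdose threshold in grams, so there is no figure to reproduce. The check is one multiplication followed by a classification.

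**Inputs**
- Part B dose: 2.1 g every 2 weeks (Sections 4.1 and 4.4)
- Limit on dosing: 2.1 g (Section 4.4)
- Multiplier: 150% (Section 8.4, closing sentence)
- Vial: 50 mg/mL with 6.0 mL extractable (Section 6.1, Table 5)

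**Threshold under the closing sentence.** 1.5 × 2.1 g = 3.15 g, which is 3.15 − 2.1 = 1.05 g above the Section 4.4 limit.

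**Vials.** 50 mg/mL × 6.0 mL = 300 mg. The Part B dose is 2100/300 = 7 vials, and the threshold is 3150/300 = 10.5 vials.

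**Classification of an accidental Part B infusion**, taking all three reference doses as 2.1 g:

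| Given | Surplus vials | % of 2.1 g | 8.4 opening | 8.4 closing | App. 2, 5.2 | Above 4.4 limit |
|---|---|---|---|---|---|---|
| 2.1 g | 0 | 100 | no | no | no | no |
| 2.4 g | 1 | 114 | overdose | no | overdose | yes |
| 2.7 g | 2 | 129 | overdose | no | overdose | yes |
| 3.0 g | 3 | 143 | overdose | no | overdose | yes |
| 3.15 g | 3.5 | 150 | overdose | no | overdose | yes |
| 3.3 g | 4 | 157 | overdose | overdose | overdose | yes |

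The wordings disagree for every amount above 2.1 g up to and including 3.15 g. For an intentional excess in that range, the two sentences of Section 8.4 still disagree, and the accidental-overdose definition in Appendix 2 does not apply.

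**Reference dose.** The three wordings refer to the dose being studied, the recommended dose level and the assigned dose. These can separate after a dose reduction, which Section 6.6 allows. As an illustration only, suppose a participant reduced to 1.2 g is given 2.1 g by mistake: 2.1/1.2 = 175% of the assigned dose.
- Appendix 2: overdose.
- Section 8.4 closing, if the recommended dose level is the 2.1 g expansion dose: threshold 3.15 g, not an overdose.
- Section 8.4 closing, if it is the participant's own level: threshold 1.5 × 1.2 = 1.8 g, overdose.

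**The case against.** Several points on the other side stand.
- There are two thresholds, not three. The opening of Section 8.4 and Appendix 2 both mean above 100%; they differ on intent and on the reference dose.
- In Section 8.4 the action list follows the opening sentence and precedes the 150% sentence. A site could fairly read the actions as starting above 100%. It cannot be said that a site following Section 8.4 would omit them, only that the text permits either reading.
- The Section 4.4 limit concerns planned dosing and does not define overdose. An infusion can exceed it without being called an overdose, so this is a tension to explain, not a third definition.
- The event would not be lost. Section 6.1.1 records the total dose given at each infusion. Section 8 asks for immediate discussion of immediate safety concerns. Appendix 2, Section 5.2 puts every medication error on the Adverse Event eCRF, with or without an adverse event. Section 9.6 lists all protocol deviations. None of these, however, supplies an overdose-specific immediate notification or settles the coding.

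A reader might also draw three stronger inferences, which the documents do not support.
- **Safety margin.** One might divide the Appendix 11 margins at 2.1 g by 1.5. Those margins are for steady state: Cmax 5835/(2 × 1355) = 2.15 and AUC (697,500 × 2)/(2 × 275,000) = 2.54, printed as 2.2x and 2.5x. Dividing by 1.5 describes sustained dosing at 3.15 g, not one error. Adding a single 1.05 g excess, scaled linearly from the 70 mg single-dose values (factor 1050/70 = 15), gives Cmax 1355 + 15 × 25.2 = 1733, margin 5835/(2 × 1733) = 1.7x, and AUC 275,000 + 15 × 3900 = 333,500, margin 697,500/333,500 = 2.1x.
- **Low-dose Part A cohorts.** One might infer that their threshold was also 3.15 g. That needs the recommended dose level to mean the expansion dose before one had been chosen. Section 4.1.2 has the model recommend a dose for each new cohort, so the cohort's own level is the more natural reading.
- **Safety tables.** One might infer that summaries by dose level are distorted. Section 9.4.3 and Table 9 plan no overdose count; exposure is summarized by duration, cycles and cumulative dose.

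**Conclusion.** The inconsistency is real and limited in extent. Section 8.4 contradicts itself, and its 150% sentence conflicts with Appendix 2, Section 5.2. In Part B the disputed range is above 2.1 g and up to 3.15 g, a band of 1.05 g that one, two or three surplus whole vials would reach. Within it, an accidental infusion is an overdose under two wordings and not under the third, and it exceeds the Section 4.4 limit. The consequence is uncertainty over whether the Section 8.4 actions apply and how the event is coded. It is not a missing record and not a bias in a planned analysis.

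The 3.15 g figure assumes that the recommended dose level in Part B is 2.1 g. The vial counts assume that whole vials are the unit of error and serve only to show that the range is reachable. Nothing here says which threshold or reference dose is right.

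**What to change.** The sponsor should reconcile both sentences of Section 8.4 with Appendix 2, Section 5.2 into one overdose definition that names one reference dose and says how it applies after a dose reduction. The text should state how that definition relates to the 2.1 g limit in Section 4.4. It should then be applied to the Section 8.4 actions and to the eCRF distinction between an accidental overdose and a medication error that does not qualify as one. The sponsor chooses the threshold and the reference dose.

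The cost is a wording change in the protocol and its appendix plus eCRF completion guidance. Depending on the choice made, a few more events might be flagged as overdose. Sample size, endpoints and planned analyses are unaffected.

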8.5 PHARMACOKINETICS

Mandatory blood samples to evaluate concentrations of study treatment will be collected from an IV line from the arm opposite to that used for study treatment administration. The date and time of each sample collection will be recorded in the eCRF. RO7121661 concentrations will be analyzed by using a validated assay. The PK samples will be taken as outlined in the SoA (see Section 1.3). During the course of the study, PK sampling time-points may be modified on the basis of emerging data to ensure the PK of RO7121661 can be adequately characterized (but without increasing overall blood collection volume for PK). This will be documented in a Note to File and a new SOA will be provided. Additional PK samples will be taken at the time of treatment discontinuation, if the participant experiences an infusion-related AE (such as an IRR), or if the participant experiences an AE leading to dose-reduction or delay of RO7121661 administration (see Section 6.6).

Remaining volumes of PK samples may also be used for additional PK/ADA analysis or assay development or validation, for RO7121661-related exploratory analyses, or to help develop further blood tests for exploratory analysis (e.g., further characterization of immune responses), after they are used for the mentioned intended use and as deemed appropriate.

The PK samples will be destroyed within 2 years after the date of final Clinical Study Report (CSR). Details on sampling procedures, sample storage, and shipment are given in the Study Flow Chart and Laboratory Manual.

8.5.1 Immunogenicity Assessments

Although RO7121661 is a human antibody, there is a risk that anti-drug antibody (ADA) against RO7121661 could develop, potentially reducing its efficacy and/or potentially resulting in symptomatic hypersensitivity reaction, in particular immune-complex reactions.

Antibodies to RO7121661 will be evaluated in blood samples collected from all participants according to the SoA (Section 1.3). Additional ADA samples should also be collected at the time of treatment discontinuation or at the safety follow-up visit and in participants who experience a Grade≥2 IRR and in participants with clinical signs of hypersensitivity reaction, in particular immune-complex reaction. In each case, for each collected ADA sample, a corresponding PK sample will be collected at the same time-point for the determination of the RO7121661 concentration.

Validated screening, confirmatory, and titer assays will be employed to detect ADAs against RO7121661. The date and time of each sample will be recorded in the eCRF. If required, ADA positive samples will be further characterized in an exploratory assay.

If required, remaining ADA samples may also be used for additional exploratory analyses (e.g., further characterization of immune responses) and/or PK/ADA assay development/validation experiments after the mentioned intended uses, as deemed appropriate.

The blood samples will be destroyed within 2 years after the date of final CSR.

Details on sampling procedures, sample storage and shipment are documented in the Sample Handling Manual.

